6.	List	of Tables	12
	6.5.	Demographic data	12
	6.6.	Descriptive Statistics	13
	6.7.	Correlation Matrices	14
	6.8.	Qualitative analysis	14
7.	List	of Figures	14
	7.5.	Box Plots	14
	7.6.	Heat-map plots	15
	7.7.	Individual Subject Trajectories	15
	Subjec	ct trajectories by time point including screening/familiarization session	15
	7.8.	Scatter plots	15
8.	Listi	ings	15
9.	Refe	erences	15
Δr	nendi	y Δ Cantah Outcome Measures	16

List of Abbreviations

[figure not shown]
CANTAB	Cambridge Neuropsychological Test Automated Battery
CI	Confidence Interval
ERT	Emotion Recognition Test
CCI	
RVP	Rapid Visual Information Processing
SWM	Spatial Working Memory
CCI	
LS	Least Squares
MMRM	Mixed Model Repeated Measures
SAP	Statistical Analysis Plan
SE	Standard Error
SD	Standard Deviation

1. Introduction

This statistical analysis plan details the methodology and data analysis procedures that will be used for reporting the results analysis of data for the Takeda MDD-5003 study.

The study is a single-arm, unblinded, 6-week prospective observational feasibility study, designed to assess the feasibility and compliance with a novel method for assessing mood and cognition in subjects with major depressive disorder (MDD). The study assesses the feasibility of and compliance with cognitive and mood testing using wearable technology and the correlation of mood and cognition outcomes on wearable technology with traditional objective neuropsychological cognitive function tests and self-reported mood outcomes. Thirty subjects aged between 18 and 65 years, inclusive, with mild-moderate depression prescribed second- or third-line antidepressant monotherapy will be recruited. Subjects will be provided with an Apple Watch on which brief cognitive and mood tests will be administered daily. Subjects will take part in up to 5 study visits, 1 in-person on-site visit, 3 web-based and 1 at home visit assessing performance on traditional objective neuropsychological cognitive function tests and self-reported measures of depression symptom severity and social function.

The co-primary endpoints are to evaluate feasibility of and subject compliance with high-frequency testing of cognition and mood on wearable technology.

Study Design - Treatment Groups and Subjects

The sample consists of 30 subjects aged between 18 and 65 years. Subjects should have a diagnosis of depression, and scores on the PHQ-9 at screening which place them in the mild-moderate range for severity (PHQ-9 score between 5 and 15). Subjects are assessed on self-reported measures and CANTAB cognitive tests at four time points: Familiarisation, Baseline, Week 3 and Week 6. Subjects will be provided with an Apple Watch at the Baseline visit and will be prompted to complete three n-back tests three times each day and a questions assessing mood and cognitive symptoms.

As the primary endpoint is compliance with cognitive testing, the full cohort will be analysed. The CANTAB data will be analysed, excluding familiarisation. The familiarisation results will be reported separately for transparency.

2. Data to be analysed

2.1. Subjects: Analysis Population

All subjects who are assessed at baseline will be included in the analysis.

2.2. Outcome Measures

The variables to be analysed are shown in Table 1 with a full description available in Appendix A.

Table 1 Outcome variables

Outcome variable	Variable code
Daily n-back compliance	nBackN
Daily mood compliance	mood
Daily watch worn	watch
N-Back d'	dprime
N-Back Hit RT	hitRT
N-Back FA RT	FART
N-Back Hit Coefficient of Variation	hitCv

Daily depressed mood	DepressedMood
Daily self-reported cognitive problems	SelfReportCognitive
Daily anhedonia	ReducedPleasure
Daily step-count iPhone	TotalStepCountlPhone
Daily step-count Apple Watch	TotalStepCountWatch
Mean daily heart rate	MeanHeartRate
Minimum daily heart rate	MinHeartRate
Maximum daily heart rate	MaxHeartRate
Standard Deviation daily heart rate	SDHeartRate
CANTAB Emotion Recognition Unbiased Hit Rate Anger	ERTUHRA
CANTAB Emotion Recognition Unbiased Hit Rate	ERTUHRD
Disgust	·
CANTAB Emotion Recognition Unbiased Hit Rate Fear	ERTUHRF
CANTAB Emotion Recognition Unbiased Hit Rate Happiness	ERTUHRH
CANTAB Emotion Recognition Unbiased Hit Rate Sadness	ERTUHRS
CANTAB Emotion Recognition Unbiased Hit Rate Surprise	ERTUHRSU
CANTAB Rapid Visual Processing A-Prime	RVPA
CANTAB Rapid Visual Processing Latency Standard Deviation	RVPLSD
CANTAB Rapid Visual Processing Latency Median	RVPMDL
CANTAB Spatial Working Memory Between Search Errors	SWMBE

CANTAB Spatial Working Memory Strategy	SWMS
CCI	CCI
CCI	CCI
CCI Total Score	CCI

3. Statistical Analysis

3.1. Descriptive Statistics

Compliance across the study will be transformed into a binary variable for mood and n-back, with days where participants completed testing coded as 1 and days with no data coded as 0. The percentage of days with data will be computed overall and by study week and tabulated.

For each subject, n-back performance across the study will be characterised by four summary variables – the mean, capturing global levels of performance, root mean square of successive differences (RMSSD), capturing variability in performance, and two measures extracted from mixed-effect modelling of the data: intercept and slope, representing initial performance and learning. These summary measures will be tabulated.

Daily mood assessment will be summarised across the study, capturing the overall level of mood across the study whole, and by study week. Means, standard deviation, RMSSD, median, number of subjects and minimum and maximum will be calculated and tabulated.

Activity data from the phone and the watch and heart rate from the watch will be aggregated by day and study week, and means, standard deviation, median, number of subjects and minimum and maximum will be calculated and tabulated.

For each of the CANTAB and PRO outcome variables, mean values, standard deviation, median, number of subjects, and minimum and maximum values will be tabulated by time point.

The output will also contain box plots/ line graphs of mean values (absolute scores) by time point, along with individual subject trajectories for each outcome variable.

3.2. Primary analysis: Compliance

Compliance with daily mood testing and daily n-back testing will be analysed separately. We will report the overall compliance (% completed testing sessions) over the six weeks of the study. The relationship between overall rates of compliance with baseline subject characteristics (CCI) will be explored through a series of bivariate correlations. These will be Pearson correlations or Spearman's rank correlation coefficient, depending on the observed distribution of the variables. As this is an exploratory study, no adjustment will be made for multiple comparisons.

will be carried out using a series of Chi-square tests.

3.2.1.Logistic Mixed-model (LMM)

We expect compliance with testing to decline over the course of the study, therefore we will use a logistic regression mixed effect model to analyse the effect of time on compliance. Day will be used as fixed factor, and subject as a random effect. We plan on testing the impact of covariates on compliance, including baseline Covariates

Covariates which do not make a significant contribution will not be carried forward. Final model will be selected on the basis of Bayes Information Criterion.

3.2.1.1. Model specification:

<< variable>=subject + day + covariate + covariate * day.

Parameters will initially be analysed without transformation, but if the data suggest otherwise, an appropriate transformation (e.g. logarithmic, square root or reciprocal) will be applied. The analysis will include the calculation of effect sizes. The assumptions of the logistic regression model will be investigated by

examining the distribution of residuals and the pattern of residuals versus fitted values. Where non-normality or non-constant variance is observed, a transformation will be applied so that the assumptions are satisfied.

Transformations will be selected by applying different transformations iteratively (e.g. logarithmic, square root, reciprocal) followed by visual inspection of the cumulative normal plot, histogram of residuals and plot of residuals vs. fitted values. The most suitable transformation in terms of normality and constant variance will be selected. If no suitable transformation can be found, then non-linear models will be considered.

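### SAP 3.2.1 selects compliance covariates by significance and then by BIC without fixing either threshold, so mixed-model covariate effects that survive from 30 subjects will tend to be too large

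*SAP*

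**What the plan says.** SAP 3.2.1 fits a logistic mixed model to daily compliance, with day fixed and subject random, to describe how compliance changes over the six weeks. It adds covariates: "We plan on testing the impact of covariates on compliance, including baseline", after which the list is cut off in the public text. The specification for each covariate is "subject + day + covariate + covariate * day", so every candidate brings a main effect and an interaction with day.

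Two selection rules follow, one after the other: "Covariates which do not make a significant contribution will not be carried forward", and "Final model will be selected on the basis of Bayes Information Criterion". The section does not state a significance level, a test, an order of entry, whether main effect and interaction are judged together, the n in the BIC penalty, or what happens when the two criteria point different ways. It does not say whether estimates for dropped covariates will be reported, and the table list in SAP section 6 has no table for the mixed model.

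Elsewhere in SAP 3.2, overall compliance rates are correlated with baseline characteristics without any selection. SAP 6.7 lists these as Tables 3.1 and 3.2.

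**The concern.** Two things are at stake. First, reproducibility: if the level of the screen and the n for BIC are open, two analysts who follow the same text can report different final models. Second, bias. A covariate measured once per subject carries information from only 30 people. If its estimate is kept only when it passes a threshold, the kept estimates are on average too far from zero, and an interval computed from the final model in the usual way takes no account of the selection.

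The study is meant to guide later work with this method (Protocol 2.0). Which characteristics go with a faster fall in compliance is a question that only the covariate-by-day terms address, and those terms appear only in the selected model. The day coefficient is also affected in meaning: once an interaction is in the model, the coefficient for day is the slope at the zero or reference value of that covariate. What it estimates therefore depends on which interactions survive.

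**Working it through.** **Inputs from the documents.** Subjects: 30 ("The sample consists of 30 subjects aged between 18 and 65 years", SAP Study Design). Duration: six weeks (SAP Introduction). Outcome: one binary value per day, "with days where participants completed testing coded as 1 and days with no data coded as 0" (SAP 3.1). Outcomes modelled: two, since "Compliance with daily mood testing and daily n-back testing will be analysed separately" (SAP 3.2).

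**Assumptions, because the SAP is silent.** The screen is two-sided at 0.05. Day enters as one linear term, and each covariate is continuous or binary, so covariate plus interaction is 2 df. All 30 subjects contribute 6 × 7 = 42 days, which gives 30 × 42 = 1,260 subject-days.

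**Nearest stated figure.** SAP 3.2.1 gives no number. Protocol 13.3 claims 80% power for r = 0.5 with 30 subjects. By Fisher's z, atanh(0.5) × √27 − 1.96 = 0.549 × 5.196 − 1.96 = 0.894, and Φ(0.894) = 81.4%. The claim reproduces under a two-sided 0.05 test.

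**Step 1: what BIC demands.** BIC keeps extra terms when the likelihood-ratio statistic exceeds df × ln(n).

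| Terms | p < 0.05 needs | BIC, n = 30 | BIC, n = 1,260 |
|---|---|---|---|
| 1 df | 3.84 | ln 30 = 3.40 (p = 0.065) | ln 1,260 = 7.14 (p = 0.0075) |
| 2 df | 5.99 | 2 × 3.401 = 6.80 (p = 0.033) | 2 × 7.139 = 14.28 (p = 0.0008) |

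On 2 df the tail area is exp(−x/2), so the equivalent p is simply 1/n: 1/30 = 0.033 and 1/1,260 = 0.0008. A covariate with its interaction and a statistic of 10 passes the screen, passes BIC with n = 30 and fails BIC with n = 1,260. On 1 df with n = 30, BIC never removes a term that passed the screen.

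**Step 2: inflation, correlation illustration.** With 30 subjects the smallest |r| with p < 0.05 is t/√(28 + t²) with t = 2.048, that is 2.048/√32.19 = 0.361. Any kept value must exceed this. In 100,000 simulated samples per row:

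| True r | Share passing | Mean absolute r when kept |
|---|---|---|
| 0.2 | 18.7% | 0.45 |
| 0.3 | 36.9% | 0.47 |
| 0.5 | 82.8% | 0.54 |

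**Step 3: inflation in the planned type of model.** This used a random-intercept logistic model with 30 subjects × 42 days and 1,500 runs per effect. Assumed values: intercept 1.9, random-intercept SD 1.2, one standard-normal covariate, no day term, and a likelihood-ratio screen at 0.05.

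| True log-odds per SD | Mean, no selection | Share passing screen | Mean when kept | Significant but rejected by BIC, n = 1,260 | Mean when kept by that BIC |
|---|---|---|---|---|---|
| 0.3 | 0.29 | 24.3% | 0.61 | 16.5% | 0.73 |
| 0.5 | 0.49 | 53.7% | 0.68 | 28.5% | 0.79 |

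Survivors of the screen are inflated by 0.61/0.3 = 2.0 times and 0.68/0.5 = 1.4 times. The stricter BIC makes this worse.

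**The case against.** A reader might infer that the two rules contradict each other. The text does not support that. The natural reading is a sequence: screen first, then let BIC choose among what remains. That gives one model once the level and n are fixed. The rules are unreconciled, not contradictory.

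A reader might also infer that later studies would receive nothing but exaggerated predictors. That is too strong as well. Tables 3.1 and 3.2 are planned to show correlations of overall n-back and mood compliance with subject characteristics, with no selection. Those tables do not show change over time, however, so they cannot replace the covariate-by-day estimates.

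Three further points have force. Inflation is small where the true effect is large: a correlation of 0.5, the value the protocol sizes for, averages 0.54 when kept. Day itself is not a candidate for removal, and the compliance percentages, overall and by week, need no model. The SAP calls the work exploratory, and Protocol 2.0 says the coprimary outcomes will be described rather than tested. The last point favours reporting every estimate with its interval. It does not favour a significance screen.

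The missing covariate list is a feature of the public text and is not counted against the plan. It does mean that the number and type of candidates are unknown here. A covariate that varies from day to day would not be limited to 30 independent values in the same way.

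**Conclusion.** The point holds with limited reach. SAP 3.2.1 leaves the significance level and the BIC n unstated. The choice of n alone moves the effective 2-df threshold from p < 0.033 to p < 0.0008. Screening subject-level covariates on significance with 30 subjects biases the survivors away from zero. Under the assumptions above, the inflation is roughly 1.4 to 2 times for log-odds effects of 0.5 and 0.3 per SD. For correlations it runs from more than double at 0.2 (0.45/0.2) to about 8% at 0.5 (0.54/0.5). The direction is secure. The sizes are illustrative, because the documents give no random-effect SD, covariate effects or screening level.

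What is affected: the mixed-model covariate and covariate-by-day estimates, and the day effect in so far as it depends on the interactions retained. What is not affected: the overall compliance percentage and the correlations in Tables 3.1 and 3.2. The issue does not undermine the coprimary compliance result, but it should be corrected before the covariate findings are used to plan another study.

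**What to change.** Replace the two selection sentences in SAP 3.2.1 with the following:

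- Report the day effect for each compliance outcome from one prespecified model without covariates, with day fixed and subject random.
- List the candidate covariates in advance. For every one, report the mixed-model odds ratio and 95% CI for the covariate and for its interaction with day, whether or not significant. State beforehand whether candidates are fitted singly or together.
- If a BIC-selected model is also shown, state the n used in the penalty and label the model exploratory.
- Add a table for these results to SAP section 6, which has none at present.

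The cost is SAP wording and a longer table. No new data, visits or subjects are needed.

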9.1.11 Wearable Technology Data

Subjects will be given an Apple Watch on which cognitive assessment and mood assessment will be carried out. Subjects will be asked to wear the watch between 8 AM and 10 PM daily for the 6-week study period. All subjects will be prompted to complete cognitive and mood assessments on 3 occasions across the day. Two occasions (morning and afternoon) will comprise assessment of cognition, and the final assessment in the evening will constitute a review of the day focusing on self-reported depressed mood. For all subjects, passive sensor data will also be acquired via the Apple Watch to assess physical activity.

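### SAP 3.2.1.1 asks a logistic mixed model of 1/0 daily compliance for normal, constant-variance residuals, which the model does not assume and no transformation of the response can supply

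*SAP*

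**What the plan says.** SAP 3.1 reduces each subject's daily record, separately for mood and n-back, to a binary variable: "days where participants completed testing coded as 1 and days with no data coded as 0". SAP 3.2.1 expects compliance to fall over the six weeks and models this with a mixed-effects logistic regression: "Day will be used as fixed factor, and subject as a random effect". Covariates and their interaction with day are also considered.

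SAP 3.2.1.1 then sets the model-checking rule, in four steps:

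- The starting point: "Parameters will initially be analysed without transformation".
- The check, introduced with "The assumptions of the logistic regression model will be investigated by", looks at how the residuals are distributed and plots them against the fitted values. No residual type is named.
- The action: "Where non-normality or non-constant variance is observed, a transformation will be applied so that the assumptions are satisfied". Log, square root and reciprocal are given as examples. The choice among them is made by eye from a cumulative normal plot, a histogram and a residual plot.
- The exit: "If no suitable transformation can be found, then non-linear models will be considered". No model is named.

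**The concern.** Normality and constant variance of residuals are assumptions of a linear model with normal errors. A logistic model has a Bernoulli or binomial response, whose variance depends on its mean by definition. Residuals from 0/1 data lie on two curves, one for each outcome, and cannot look normal. The SAP therefore names the wrong properties as the assumptions of its model.

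An analyst who applies the rule as written will see a failure whether or not the model is right, will find no transformation that helps, and will then be considering unnamed alternatives with the data in view. An analyst who sets the rule aside departs from the SAP. Either way, the rule says nothing about whether the model fits. What is at stake is the estimated decline in compliance over time and the covariate effects on it.

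**Working it through.** The plan gives no figure on this point, so there is none to reproduce. The check has four steps.

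**Inputs from the documents.** Outcome 1/0 per subject per day (SAP 3.1); logistic mixed model with day fixed and subject random (SAP 3.2.1); 30 subjects (SAP, Study Design); six weeks, so 6 × 7 = 42 days; 80% compliance as the only planning rate (Protocol 13.3). The rates of 70% and 90% are assumed, to bracket it.

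**1. Residuals of a correct model, exactly.** For a 0/1 outcome with true probability p, the raw residual y − p has variance p(1 − p) and skewness (1 − 2p)/√[p(1 − p)].

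| Fitted compliance p | Variance | Skewness |
|---|---|---|
| 0.70 | 0.70 × 0.30 = 0.21 | −0.40/0.458 = −0.87 |
| 0.80 | 0.80 × 0.20 = 0.16 | −0.60/0.400 = −1.50 |
| 0.90 | 0.90 × 0.10 = 0.09 | −0.80/0.300 = −2.67 |

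The variance changes by a factor of 0.21/0.09 = 2.33 between 70% and 90%. Dividing by the binomial standard deviation (Pearson residuals) equalises the variance but not the shape. At p = 0.80 the residual can only be (1 − 0.80)/0.40 = +0.5 or (0 − 0.80)/0.40 = −2.0.

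**2. The listed transformations.** Applied to y = 0 and y = 1:

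- log: undefined at 0
- reciprocal: undefined at 0
- square root: 0 and 1, unchanged
- log(y + 1): 0 and 0.693
- 1/(y + 1): 1 and 0.5
- √(y + 0.5): 0.707 and 1.225

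Any finite transformation g of a two-valued outcome satisfies g(y) = g(0) + [g(1) − g(0)]·y, which is a linear rescaling. The variance ratio stays at 2.33 and the absolute skewness at p = 0.80 stays at 1.50. This holds for any other transformation too, so it does not matter that the SAP's list is only illustrative. A response recoded to values other than 0 and 1 also no longer fits a logistic likelihood. Transforming covariates instead would leave the outcome two-valued.

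**3. Simulation with the correct model fitted.** Data for 30 subjects × 42 days were generated from a random-intercept logistic model, and the same model was fitted by maximum likelihood. Assumed inputs, not in the documents: day slope −0.02 on the logit scale, random-intercept SD 0.5 or 1.0, intercepts 1.0, 2.2 and 3.4. These gave four scenarios with mean compliance of 62%, 82%, 84% and 93%, with 100 runs each. The SAP's check is visual; tests at 5% stand in for it here (Shapiro-Wilk for normality, squared residual regressed on fitted value for constant variance).

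| Residual type | Normality rejected | Constant variance rejected |
|---|---|---|
| Raw | 100% | 97–100% |
| Pearson | 100% | 27–85% |
| Deviance | 100% | 97–100% |
| Randomised quantile | 4–8% | not tested |

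The variance of raw residuals in the lowest quartile of fitted values was 2.0 to 20 times that in the highest.

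**4. If session counts were modelled instead.** With 2, 3 or 9 sessions a day (40 runs each), normality was again rejected in 100% of runs for raw, Pearson and deviance residuals.

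**The case against.** **The SAP names no residual type.** Randomised quantile residuals behave as they should under a correct model, so the check need not fail for every conceivable residual. This stands as a qualification. Nothing in the SAP points to such residuals, however, and a rule to transform until the plots look normal belongs to the linear model. The constant-variance half of the check is also less certain to fail if Pearson residuals are used.

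**The outcome might be session counts.** Protocol 13.1.3 and SAP 3.2 also speak of proportions of assessments or sessions. For mood, the protocol has one evening prompt a day, so the outcome is 0/1 on either reading. For n-back, the protocol has "Two occasions (morning and afternoon) will comprise assessment of cognition, and the final assessment in the evening", whereas the SAP has subjects "prompted to complete three n-back tests three times each day", so a daily count would not be two-valued. Normality and constant variance would still be the wrong criteria for a binomial model. A reader might go further and infer that the listed transformations make the residuals of counts worse. The documents do not support that, because the result depends on what is transformed. With 2 sessions a day, the 70% v 90% variance ratio moves from 2.33 to 3.04–4.29 if completed sessions are transformed, but to 1.80–1.98 if missed sessions are.

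**The fallback is permissive.** The SAP says that non-linear models will be considered, and a logistic mixed model is already non-linear in its mean. A reader might infer that the SAP obliges the analyst to give up a correct model. It does not say that. What stands is that the exit has no content and is reached only after the data have been inspected.

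**Day as a factor.** A reader might take the word factor to mean 42 separate day categories, with unstable estimates. That reading is strained: the sentence most naturally contrasts fixed with random, and the stated aim is to model decline over time. No weight is put on it here.

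**Conclusion.** The rule in SAP 3.2.1.1 is wrong as written for the model it governs. With the 1/0 outcome, raw, Pearson and deviance residuals fail normality when the model is correct (100% of simulated runs), raw variance differs 2.33-fold between 70% and 90% compliance, and no transformation of the response changes either feature. The algebra is exact and needs only that the 1/0 code of SAP 3.1 is what is modelled. The simulated percentages rest on the assumed slope, intercepts and random-intercept SD.

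A reader might infer that the primary compliance result is unsound. The documents do not support that. The compliance percentages are computed directly from the records and do not use this model. No success criterion depends on it, and Protocol 2.0 says that adherence rates will be described without inferential statistics. The effect is confined to the exploratory estimates of time and covariates. The correction should be made because the error is clear and cheap to remove.

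**What to change.** For this model, replace the text on normality, constant variance and transformation of the response with wording such as:

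*Daily compliance (1/0) will be analysed untransformed with a binomial logistic mixed model. Fit will be checked with methods suited to binary data, for example simulated quantile or binned residuals, and observed versus predicted compliance by study week.*

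Replace the open-ended fallback with a named one for a trend that is not linear on the logit scale, such as study week as a categorical term, or a quadratic or spline term in day. Simply deleting the fallback would leave no provision for a curved trend. If n-back session counts are to be modelled, say so and state the number prompted per day as the binomial denominator, since the protocol and SAP differ on it.

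The cost is a few lines of SAP text and a short diagnostic program. No new data are needed and the descriptive results do not change.
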